### **Randomization and Allocation Concealment:**

Participants will be randomized into three parallel groups with an equal allocation ratio of 1:1:1 using a computer-generated randomization list created with GraphPad QuickCalcs. Allocation concealment will be achieved using sequentially numbered, opaque, sealed envelopes (SNOSE) prepared by an independent researcher not involved in recruitment. Each envelope will contain:

1. A group allocation card (A, B and C).
2. The assigned oral hygiene product in an opaque sealed bag.
3. Written instructions for product use.

Envelopes will remain sealed until the day of bonding, at which point the clinician will open the envelope to reveal the participant's group and provide the assigned intervention. The allocation list will be securely stored by the independent researcher and will not be accessible to the study team until after data collection and primary

statistical analysis are completed.

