## **Methodology**

### **Study Design:**

This study is designed as a multicenter, parallel, randomized clinical trial. Each participant will be randomly assigned to one of the three groups:

- **Group A:** Participants will be instructed to brush their teeth three times daily with the hydroxyapatite-containing toothpaste and to rinse twice daily with a placebo mouthwash.
- **Group B:** Participants will be instructed to brush their teeth three times daily with a conventional fluoride toothpaste and to rinse twice daily with a hydroxyapatite-containing mouthwash.

- **Group C:** Participants will be instructed to brush their teeth three times daily with a conventional fluoride toothpaste and to rinse twice daily with a placebo mouthwash.

All interventions and assessments will be conducted throughout the study period. The same participant (orthodontic patient) will be evaluated at baseline (before bonding) and at 1, 3, and 6 months after the placement of orthodontic appliances.

Participants will receive standardized oral hygiene instructions, and all assessments of white-spot lesions will be performed using Diagnodent Pen, Gorlick index (GI), digital photographs, Gingival Bleeding Index (GBI), Plaque Index (PI), and salivary pH measurements to minimize variability and ensure consistent data collection.

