### **Settings:**

The study will be conducted at the Department of Orthodontics, University of Baghdad, as well as in selected private and public dental clinics that provide fixed-appliance orthodontic treatment. All participants will be treated using conventional metal brackets to ensure standardization of the orthodontic appliance type. All procedures, including oral examinations and sample collections, will follow standardized protocols to ensure consistency and uniformity across all study sites.

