### **Sample Size:**

The sample size for the present study was determined to provide 80% statistical power at a 5% significance level ( $\alpha = 0.05$ ) to detect a 1-unit difference in the decalcification index (Gorlick index) (**Hoffman et al, 2014**). Accordingly, the current study will include a total of 75 participants, equally distributed into three groups of 25 subjects each, to ensure adequate statistical power and to account for potential dropouts.

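### Multicentre trial with an allocation scheme that gives centre no role: arms are likely to be uneven within clinics, and some precision can be lost

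*Protocol*

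**What the plan says.** Protocol, Study Design: "This study is designed as a multicenter, parallel, randomized clinical trial". Protocol, Settings: recruitment is at the University of Baghdad orthodontic department "as well as in selected private and public dental clinics that provide fixed-appliance orthodontic treatment". The number of clinics is not given.

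Protocol, Randomization and Allocation Concealment: three groups at an "equal allocation ratio of 1:1:1", "using a computer-generated randomization list created with GraphPad QuickCalcs". Concealment uses "sequentially numbered, opaque, sealed envelopes (SNOSE) prepared by an independent researcher not involved in recruitment". The clinician opens the envelope on the day of bonding and finds a card marked A, B or C. The list is mentioned again in the singular: "The allocation list will be securely stored by the independent researcher". The section does not mention blocks, strata, minimisation, centre, or how envelopes are shared among clinics.

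Protocol, Sample Size: 75 participants, 25 per group, for "80% statistical power at a 5% significance level" to detect a difference of 1 unit on the Gorelick index. No standard deviation and no dropout rate are stated.

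**The concern.** University, private and public clinics can draw patients with different backgrounds, so clinic may explain part of the variation in white-spot outcomes. If allocation takes no account of clinic, chance decides how the three arms divide within each one. An analysis that ignores clinic then carries the between-clinic variation as noise. An analysis that adjusts for clinic loses information wherever the arms are uneven. With 25 per arm there is little to spare.

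A statistical analysis plan that is not shown may well add centre to the model. It cannot supply the allocation scheme, which must be settled before the first participant and which the protocol sets out in this section.

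**Working it through.** **The plan's own figure.** The 75 cannot be reproduced, because the standard deviation (SD) and dropout rate are missing. Solving backwards (two-sided 5%, normal approximation, no dropout): SD = 1 / (√(2/25) × (1.960 + 0.842)) = 1.26. This SD is an assumption, chosen so that 25 per arm gives exactly 80% power for 1 unit.

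**Assumed inputs.** 3, 5 or 10 centres; centre explaining 1%, 5%, 10% or 20% of outcome variance; overall arms of exactly 25/25/25. The last assumption favours the protocol, since the text does not exclude simple randomisation.

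**Step 1: imbalance within clinics** (random permutations of a 25/25/25 list).
- Some centre has one arm at least twice as large as another: about 52% of the time with 3 centres of 25, and 96% with 5 centres of 15. A 6/6/3 split already counts.
- Some centre has a gap of 4 or more between its largest and smallest arm: 83% and 91%.
- Some centre has an empty arm: 0% and 1%, but 72% with 10 centres of 7 or 8.

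**Step 2: information kept by a centre-adjusted A v B comparison.** With a and b participants of the two arms in a centre, information is Σ ab/(a+b), against 12.5 under perfect balance. For a centre holding m of the 50 participants, the expected value of ab/m is (m − 1) × 25 × 25 / (50 × 49). Summing over K centres and dividing by 12.5 gives (50 − K)/49:
- K = 3: 47/49 = 96% (5th percentile by simulation 88%)
- K = 5: 45/49 = 92% (5th percentile 81%)
- K = 10: 40/49 = 82%

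A model fitted to all three arms loses less: about 97%, 94% and 87% is kept.

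**Step 3: power for a pairwise contrast.** With centre adjustment, power = Φ(2.802 × √(I / (1 − ρ)) − 1.960), where I is the share of information kept and ρ the share of variance due to centre. Balanced allocation has I = 1. In the three-arm model:

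| ρ | Balanced, adjusted | Unstratified, adjusted: 3 centres | 5 centres | 10 centres | Unstratified, unadjusted |
|---|---|---|---|---|---|
| 0.01 | 80.4% | 79.3% | 78.1% | 74.9% | 80.0–80.1% |
| 0.05 | 82.0% | 80.9% | 79.7–79.8% | 76.6% | 80.2–80.6% |
| 0.10 | 84.0% | 82.9% | 81.8% | 78.8% | 80.3–81.3% |
| 0.20 | 87.9% | 87.0% | 86.1% | 83.3% | 80.7–82.5% |

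The gap between the balanced column and the unstratified, adjusted columns is what stratification alone adds: about 1 point with 3 centres and 2 with 5. Using only the two arms compared (step 2), the same formula gives 1.4 to 1.7 points with 3 centres and 2.8 to 3.4 with 5. For example, at ρ = 0.05 with 5 centres, 2.802 × √(0.918/0.95) − 1.960 = 0.795, so power is 78.7% against 82.0%. The 10-centre losses are slightly overstated, because centres of 7 or 8 cannot be split exactly in three.

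**Step 4: if centre is ignored.** The variance of an arm contrast exceeds that under balance with adjustment by about 1%, 4–5%, 8–10% and 17–23% at ρ = 0.01, 0.05, 0.10 and 0.20.

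**The case against.** The strongest reply is that the protocol is silent rather than wrong. It does not deny blocking, and arms of exactly 25 suggest some overall restriction. That stands as far as it goes. It does not supply any role for centre, and overall restriction does not balance arms within a clinic.

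Centre effects may also be small. Entry is limited to patients with good hygiene and normal salivary measures, visible caries and enamel defects are excluded, and brackets, instructions and the DIAGNOdent examiner are standardised. This stands too: nothing in the protocol supports a figure as high as 20% of variance.

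Three stronger readings are tempting, and the documents do not support them.
- *A numbered series must be cut into runs per clinic, which weakens concealment.* The protocol has one investigator take all photographs and one examiner take all DIAGNOdent readings. Staff who travel between clinics could carry one series and open it in order. The text does not say how envelopes are held, so no concealment defect follows.
- *Stratifying the list lifts power from 80% to 82%, 84% or 88%.* Those figures combine stratification with centre adjustment. With 3 centres most of the rise at ρ = 0.10 or 0.20 comes from adjustment, which an analysis plan could add by itself.
- *The comparison is biased.* Unstratified random allocation is unbiased. Imbalance within clinics affects precision only.

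Finally, blocking has a price here. The clinician sees the A, B or C card, so within a small clinic the next letter can sometimes be guessed.

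**Conclusion.** The point holds as a modest and cheap gain in precision, worth making before recruitment starts. It is not a validity error. The trial is multicentre, the scheme described is a single list, and centre plays no stated part in it. With 75 participants, uneven arms within clinics are likely. The cost is roughly 1 to 3 power points with 3 to 5 centres if the analysis adjusts for centre, and more with many small clinics. If centre is ignored and explains very little variance, the cost is close to nil. All sizes rest on the assumed number of centres, the assumed centre variance, an SD of about 1.26, no dropout, and overall arms of 25 each.

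**What to change.** In Protocol, Randomization and Allocation Concealment, before the first randomisation:
1. State the number of centres and how envelopes are held and released at each.
2. Replace the single list with one list per centre, pooling very small clinics into one stratum.
3. Use permuted blocks of randomly mixed sizes (for instance 3 and 6), with the sizes kept from the clinics and out of any document they hold.
4. Number the envelopes separately within each stratum.
5. Include the stratum as a factor in the primary comparison. Without that term, the reported standard errors do not reflect the balance gained.

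The cost is a regenerated list and a few sentences of protocol text; the total of 75 does not change. Incomplete last blocks may move the arm totals slightly away from 25/25/25. Predictability rises somewhat because the group card is visible to the clinician, so the sizes must be mixed and withheld. If blocking by centre was already intended, this section needs only to say so.

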### **Blinding:**

This study will be conducted under a double-blind design. Both the principal investigator and the participants will be blinded to group allocation. The toothpaste and mouthwash bottles will be coded and identical in appearance, color, and packaging, ensuring that neither the clinician nor the participant can identify which formulation (hydroxyapatite-containing or conventional) is being used. The code will be kept by an independent researcher who is not involved in the study procedures or data analysis and will only be revealed after the completion of data collection.

All clinical assessments, including Gorelick Index (GI), Diagnodent Pen measurements, digital photography, Gingival Bleeding Index (GBI), Plaque Index (PI), and salivary pH, will be conducted without knowledge of participants' assigned group.

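### The envelope card tells the clinician the treatment arm, although the protocol says the clinician cannot identify the formulation

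*Protocol*

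**What the plan says.** Protocol, Randomization and Allocation Concealment: allocation uses "sequentially numbered, opaque, sealed envelopes (SNOSE) prepared by an independent researcher not involved in recruitment". The first item listed in each envelope is "A group allocation card (A, B and C"), followed by "The assigned oral hygiene product in an opaque sealed bag" and written instructions. On the day of bonding, "the clinician will open the envelope to reveal the participant's group and provide the assigned intervention".

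Protocol, Study Design and Procedure / Intervention define the letters by product:

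- A: hydroxyapatite toothpaste and placebo rinse.
- B: fluoride toothpaste and hydroxyapatite rinse.
- C: fluoride toothpaste and placebo rinse.

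Mouthwash Protocol repeats the rinse for each letter and marks C as the control.

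Protocol, Blinding: the trial is called double-blind. "Both the principal investigator and the participants will be blinded to group allocation". Toothpaste and mouthwash are coded and look alike, "ensuring that neither the clinician nor the participant can identify which formulation (hydroxyapatite-containing or conventional) is being used". A person outside trial conduct and analysis holds the key to the product codes. All six listed assessments (Gorelick Index, DIAGNOdent, photography, gingival bleeding, plaque and salivary pH) "will be conducted without knowledge of participants' assigned group".

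**The concern.** The opaque bag and the matched bottles hide the product, but the card beside them names the group in letters that the protocol decodes. A clinician who knows the protocol therefore learns both products on reading the card. The trial would then be reported as blinding the clinician while its own procedure does the opposite.

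Two further matters depend on this. If that clinician also photographs, grades or measures, outcome assessment is no longer blind. This matters most for the Gorelick Index, which is a visual judgement, a primary-objective measure and the basis of the sample size. Also, a clinician who knows the arm can pass that knowledge on to the participant. The documents show neither of these happening, but the written procedure leaves both open.

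**Working it through.** No power or effect calculation applies. The check is to set the sections side by side and count what they state.

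**Step 1: what the clinician learns.**

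| Element | Where in the protocol | Does it hide the arm from the clinician? |
|---|---|---|
| Sealed, numbered envelope | Randomization and Allocation Concealment | Yes, until it is opened |
| Opaque bag | Randomization and Allocation Concealment | Hides the product, not the letter |
| Coded, identical bottles | Blinding | Hide the product, not the letter |
| Group card, A, B or C | Randomization and Allocation Concealment | No: the letter is defined in Study Design, Procedure / Intervention and Mouthwash Protocol |

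Concealment before assignment is intact. The failure is in blinding after assignment.

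**Step 2: how often.** Sample Size gives three groups of 25, and there is one envelope per participant. 3 × 25 = 75 openings, and each shows a defined letter, so 75 of 75. Settings lists several sites, so more than one clinician may be involved.

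**Step 3: whether the assessors are kept apart from the disclosure.** Blinding lists six assessments.

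- A single person is specified for 2: one investigator takes the photographs (Photography and Gorelick Index Assessment), and one trained examiner takes the DIAGNOdent readings (the DIAGNOdent section).
- Nobody is specified for 6 − 2 = 4: Gorelick grading, gingival bleeding, plaque and salivary pH.
- The assessor is stated to be someone other than the clinician who opens envelopes for 0 of 6.

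This counts what the text states. It does not show that the roles overlap. The protocol also calls the principal investigator blinded without saying whether that person opens envelopes.

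**Step 4: when the key is released.** The randomization section withholds the allocation list from the study team until the primary analysis is finished. The blinding section releases the code once data collection ends. The text does not say whether these are one record or two, so this is an unclear point and not a contradiction.

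**The case against.** The best defence is that the card letters were meant as masked codes. Coding the products and withholding the list make little sense if the card gives the arm away, so loose drafting is plausible. But no section says the letters are masked. The same three letters label the card and the openly defined arms, and the stated purpose of opening the envelope is to reveal the group. Equating the two sets of letters is an inference, though it is the natural reading. If masking was intended, the protocol still has to say so.

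A second objection is that the sentence on being blinded to allocation covers only the principal investigator and the participants, and that the clinician appears only in the next sentence, about formulation. That is correct, but the next sentence is explicit about the clinician. Since the letter identifies the formulation, the conflict remains.

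Third, assessor blinding is promised outright, and it can be kept even if the clinician who dispenses the products knows the arm. This stands. If several clinicians open envelopes while one person photographs and one takes the DIAGNOdent readings, opener and assessor cannot coincide for every participant. Overlap for some participants remains possible. The objection limits the finding to the clinician's blind plus an unresolved risk for assessment.

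Finally, 75 of 75 describes how far the disclosure reaches, not how much harm it does. That is accepted.

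**Conclusion.** The concern holds. As written, the envelope procedure and the blinding statement cannot both be carried out: the clinician is told the arm at all 75 assignments and is also said to be unable to identify it. This rests on one assumption, that the card letters are the same A, B and C that the protocol defines. Nothing in the protocol says otherwise.

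Loss of the participants' or assessors' blind is not established, and no number of affected readings and no size of bias is claimed. The point still has to be settled before the trial starts, because disclosure cannot be reversed for a participant once the envelope has been opened.

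**What to change.** Preferred change, in Randomization and Allocation Concealment:

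- Remove the group card and the wording about revealing the group.
- Label each participant's identical products with a unique kit number. The existing sequential envelope number can serve, and the same number should go on any resupply.
- The independent researcher holds the key linking kit number to arm.
- Unique kit numbers carry no grouping, so that researcher supplies three masked labels, unrelated to A, B and C, for the primary analysis. The true arms are disclosed after it, as the section already provides for the allocation list.

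In Blinding, state that nobody who photographs, grades or measures outcomes opens an envelope that discloses the arm. Say how the allocation list and the code relate, and give a single release time if they are the same record.

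Alternative: keep the card, stop describing the clinician as blinded, and have the envelopes opened by someone who assesses no outcomes.

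The preferred change costs edits to two sections, number labels in place of cards, and one file of masked labels from the researcher who already prepares the envelopes. The alternative costs a fixed separation of roles and a weaker blinding claim in the report. Neither adds participants, visits or measurements, and neither changes treatment.

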### **Blinding:**

This study will be conducted under a double-blind design. Both the principal investigator and the participants will be blinded to group allocation. The toothpaste and mouthwash bottles will be coded and identical in appearance, color, and packaging, ensuring that neither the clinician nor the participant can identify which formulation (hydroxyapatite-containing or conventional) is being used. The code will be kept by an independent researcher who is not involved in the study procedures or data analysis and will only be revealed after the completion of data collection.

All clinical assessments, including Gorelick Index (GI), Diagnodent Pen measurements, digital photography, Gingival Bleeding Index (GBI), Plaque Index (PI), and salivary pH, will be conducted without knowledge of participants' assigned group.

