### Stopping Roles:

- Any patient developing severe adverse reactions to the products.

- Patient withdrawal of consent.

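### The blinding rules make no exception for the severe product reactions the protocol foresees, and a shared arm letter on a card the clinician opens may undo the blind

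*Protocol*

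**What the plan says.** Four parts of the protocol bear on this.

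- **Blinding.** An independent researcher holds the code, which "will only be revealed after the completion of data collection". On the products: "The toothpaste and mouthwash bottles will be coded and identical in appearance, color, and packaging". The section concludes that neither clinician nor participant can tell which formulation is in use. It does not say whether a bottle's code is unique to a participant or common to an arm.
- **Randomization and Allocation Concealment.** The allocation list "will not be accessible to the study team until after data collection and primary" analysis is finished. Each envelope holds "A group allocation card (A, B and C", together with the product and written instructions. On the day of bonding "the clinician will open the envelope to reveal the participant's group and provide the assigned intervention".
- **Stopping Roles.** The first entry is "Any patient developing severe adverse reactions to the products". Nothing is said about disclosing the allocation, or about whether product use or trial participation stops.
- **Study Design, Procedure / Intervention and Mouthwash Protocol.** Study Design and Procedure / Intervention spell out what A, B and C receive: A has hydroxyapatite toothpaste and placebo mouthwash, B has fluoride toothpaste and hydroxyapatite mouthwash, and C has fluoride toothpaste and placebo mouthwash. Mouthwash Protocol repeats the mouthwash part under the same letters.

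**The concern.** The protocol anticipates an event in which a treating clinician may need to know what one patient has been using, and its own wording rules that disclosure out. This is more than silence: the Blinding section sets a timing rule without exception, and the allocation section adds a second, longer bar. Emergency disclosure belongs in a protocol's blinding section, so it is not a detail that can be left to a statistical analysis plan. The timing of the final code break is not in dispute here.

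The second issue is how the allocation is labelled. The only identifier described is a letter common to everyone in the arm. Depending on what that letter means to the person who reads it, either the blind is already lost for the clinician at bonding, or one emergency disclosure could carry information about many other participants. Both outcomes weaken a trial whose primary measures include examiner-dependent readings.

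**Working it through.** **Arm size.** The Sample Size section gives "a total of 75 participants, equally distributed into three groups of 25 subjects each", and the allocation section gives an "equal allocation ratio of 1:1:1". Then 75 / 3 = 25 per arm, as stated.

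**How long the bars last.** Durations are from the Timetable: recruitment and screening 1 month, intervention and follow-up 6 months, data analysis 1 month.

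- Code (Blinding section): 1 + 6 = 7 months from the opening of recruitment.
- List (allocation section): 1 + 6 + 1 = up to 8 months, if the primary analysis takes the whole analysis month.

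The two sections therefore also differ from each other on when allocation becomes known.

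**The rules against the foreseen event.**

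| Section | Rule | Exception for a severe reaction |
|---|---|---|
| Blinding | Code revealed only once data collection is complete | None stated |
| Randomization and Allocation Concealment | List closed to the study team until the primary analysis is also complete | None stated |
| Stopping Roles | Severe product reaction is listed | No mention of disclosure |

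**What the letter reveals.** There are two cases, and the protocol does not say which applies.

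1. *The card uses the printed letters.* The clinician reads the letter at bonding, and the protocol states what each letter means. The clinician then knows the allocation of every participant whose envelope he or she opens, with no code break. This contradicts the Blinding section.
2. *The letters are masked*, so that their meaning is known only to the independent researcher. The exposure from one disclosure then depends on the bottle code, which is not described:
   - If the letter is the only code, decoding it for one participant decodes it for that arm: up to 25 of 75, and 25 / 75 = 33%. The other 75 − 25 = 50 are narrowed from three possible arms to two. A second disclosure in a different arm would settle all 75.
   - If bottle codes are unique to each participant and disclosure is made through them, 1 of 75 is exposed, and 1 / 75 = 1.3%.

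The figure of 25 is a maximum. It counts only participants whose letter is known to the person who learns its meaning, and the trial is multicentre, so one clinician may know few of them.

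**What disclosure would tell the clinician.** Every participant uses a toothpaste and a mouthwash. Disclosure names one of three pairs. It does not say which member of the pair caused a reaction.

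**The case against.** The strongest reply has four parts.

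*The bottle code may already be per participant.* The envelopes are sequentially numbered and each holds one participant's product, so the packaging does not rule out individual disclosure. This stands. A reader might infer that the products are coded by arm letter and that one break necessarily exposes 25 people. The protocol documents the letter for the allocation card only, so that inference goes too far.

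*If the clinician already knows the arm, no disclosure is needed.* True in the first case above, but then the blinding claimed for the clinician fails. The reply exchanges one defect for another.

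*The safety gain is limited.* A reader might infer that the ban prevents the causative product from being identified. The documents do not support that: disclosure gives the pair, and the stopping entry applies to any patient whatever the arm. The protocol gives no expected reaction rate, and its background section describes the hydroxyapatite toothpaste evidence as free of adverse effects. This limits the size of the problem. It does not remove the conflict between a listed event and a rule without exceptions.

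*Harm to outcome assessment is speculative.* A reader might infer that one person scores every outcome and would be unblinded by a disclosure. The DIAGNOdent section names a single examiner for its measurements, and the photography section a single investigator for capturing the images. Neither says that one person scores the Gorelick, plaque and bleeding indices as well, and nothing says that a disclosure to a treating clinician would reach an examiner. The risk is therefore conditional.

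**Conclusion.** The concern holds in a limited form. On the text, disclosure of one participant's allocation is barred throughout data collection, about seven months from the opening of recruitment, although severe product reactions are foreseen. The Blinding, Randomization and Allocation Concealment, and Stopping Roles sections must be reconciled.

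The labelling problem holds in one of two ways, and the protocol must say which. With the printed letters on the card, the clinician is unblinded from bonding. With masked letters as the only code, one disclosure could expose up to 25 of 75 participants, as an upper bound. With participant-level bottle codes it exposes one. The first way assumes that the card's letters have the meaning printed elsewhere in the protocol; the second assumes masked letters and no other code.

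This should be corrected, preferably before enrolment. It is not fatal to the trial: the number of reactions to expect is not given and may be small, and nothing here alters the sample size or the planned comparisons.

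**What to change.** 1. **Disclosure.** Amend both the Blinding and the Randomization and Allocation Concealment sections, since changing one would leave the other bar in place. After a severe reaction, the independent researcher who already holds the code may disclose that one participant's products to the treating clinician only. Date and reason are logged, and outcome assessors stay blinded.
2. **Labels.** Replace the A/B/C card, and any product code shared within an arm, with participant-numbered codes. The key stays with the independent researcher. The clinician who opens the envelope then sees a number, and one disclosure concerns one participant.
3. **Release time.** State a single point at which the code and the list become available, since the two sections now differ.
4. **Analysis.** State that a participant whose allocation is disclosed stays in the randomised group for analysis.
5. **Stopping Roles.** The sponsor should clarify whether the entry on severe reactions refers to product use or to participation. That is a clinical decision and is not settled here.

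The cost is a few sentences, different labels and a disclosure log. No visits, staff or participants are added.
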